This Appendix describes the continuation of the 3 Dynamic Prevention Randomized studies (refer to section 9.2.1 of protocol) for a 48 week follow up period following re-consent for this CAB-LA extension. Persons who are already enrolled in the trials and were randomized to the intervention arm will be eligible to receive CAB-LA as one of the options in the “Dynamic prevention” model. Persons in the control arms will be eligible to receive CAB-LA if and when it is rolled out through in country programs. If CAB-LA is not available in country at the 48-week endpoint, all participants in the intervention arm will have the opportunity to continue in the study until Week 96, and participants who are currently on CAB-LA may continue through the extension. The study will end at Week 96, and by that time participants will be transitioned to in country prevention care. At 96 weeks, persons on CAB-LA will be transitioned to in country CAB-LA or to other prevention options if CAB-LA is not available. Prior to this transition, available in country options will be assessed by the study team. HIV prevention options will be discussed with each study participant by their Week 88 visit, with a plan established for the transition to the participant’s preferred prevention method in coordination with local health facilities to avoid interruption after their 96 weeks of study participation is completed.

The overall purpose of this extension is to 1) Determine if adding the option of CAB-LA as a prevention choice using a patient-centered HIV prevention delivery model increases prevention coverage (i.e. proportion of time that is covered by a biomedical prevention option, such as PrEP or PEP) compared to the standard-of-care in 3 ongoing randomized trials of Dynamic Choice Prevention in rural Uganda and Kenya; and, 2) Conduct a hybrid implementation study (Primary Objective Clinical and Secondary Objective Implementation) focusing on initial implementation of a patient-centered model for CAB-LA using the RE-AIM evaluation framework among persons randomized to the intervention arms.

A. Background and Rationale

Background: SEARCH Sapphire is an ongoing, NIH-funded study that is testing multi-disease and multi-sector interventions aimed at reducing HIV burden and improving health in rural Uganda and Kenya. Phase A is a portfolio of randomized prevention and treatment implementation studies that will inform a population-level study in Phase B (refer to section 3.0 of protocol).

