At the time of writing of this protocol version, the standard of care for both Kenya and Uganda is to offer biomedical prevention as part of the HIV prevention package that includes provision of PrEP for persons at risk of HIV acquisition, such as persons with partners living with HIV or of unknown HIV status, or those with a history of exchange/transactional sex, recent STIs, or recurrent use of PEP (more than 3 times a year). PEP is offered primarily after occupational exposures or in cases of sexual assault. For participants consenting in the extension, in the control arm, they will continue to be seen by government staff in the HIV clinic or other service location, like a drop-in centre, and receive prevention interventions according to standard of care guidelines recommended by the country's Ministry of Health. There will be no change to their HIV prevention healthcare (refer to section 9.2.1.5 of protocol)

Control participants will be seen for a study visit every 24 weeks for HIV testing (RNA and rapid), weight, and a survey on which prevention method(s) they have been using and self-reported risk. If control participants report using medications such as PrEP or PEP at the interim visits, they will be asked to provide hair, blood, or urine samples in order to measure HIV prevention medication levels.

For intervention participants who do not choose CAB-LA, there will be study visits every 12 weeks (refer to section 9.2.1 of the protocol); however, they can decide to begin CAB-LA at any time during the initial 48-week extension. Participants will not be able to initiate or restart CAB-LA in the additional extension period between Week 48 and Week 96; only those who are taking CAB-LA at the time of the Week 48 visit may continue. Intervention participants that choose CAB-LA will have study visits that align with their injection visits (every 4 weeks for the first two months and then every 8 weeks thereafter), but can return to an alternate DCP intervention if they decide to stop CAB-LA.

For participants that select CAB-LA, the extension visits will also include (Table 6):

- A separate qualitative interview (At time of CAB-LA start, Week 24 and Week 48)
- Safety Labs:
 - HBsAg at baseline
 - ALT at Weeks 0 and 24; optionally at Weeks 8 and 48
- Pregnancy tests
- In addition to the Week 24 and 48 extension visits, injection visits will occur in clinic every 4 weeks for the first two months and then every 8 weeks thereafter

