- HIV-RNA Cepheid test at baseline, Week 24, Week 48, Week 72, Week 96 and reinduction
- Plasma will be stored at each visit for future use to evaluate use of alternate HIV assays and cabotegravir PK. Small hair samples will be stored at visit weeks 8, 24, 32, and 48 to assess cabotegravir PK.
- Participants that stop CAB-LA prior to the end of the extension time period will continue to be followed in the study but *not* be actively followed beyond the 96 week followup time of the study.
 - Oral PrEP (TDF/3TC) will be recommended to cover tail
 - Participants will switch back to Q12 week follow-up

Table 5. Schedule of Evaluations Dynamic Choice Prevention Extension – Baseline to Week 48

	Screening/ Baseline	Week 12	Week 24	Week 36	Week 48 ⁴
DCP Intervention (For persons not receiving CAB-LA)¹					
Study visit	X	X	X	X	X
DCP intervention, including:	X	X	X	X	X
- Offer PrEP, PEP, prevention options ²	X	X	X	X	X
- HIV testing options	X	X	X	X	X
- Visit location choice	X	X	X	X	X
- Structured assessment of barriers	X	X	X	X	X
- GBV screening	X		X		X
HIV self-test (alternative to rapid)		X	X	X	
Rapid (blood-based) HIV test	X	X	X	X	X
STI symptom screen	X	X	X	X	X
Pregnancy testing (optional)	X	X	X	X	X
DCP (including those persons on CAB-LA) and SOC					
Measure height (baseline only) and weight	X		X		X
Assess self-reported PrEP/PEP use and HIV risk over prior 6 months	X		X		X
Complete Week 24 or 48 Visit eCRF			X		X
Hair sample collection if any PrEP or PEP doses taken in last 30 days			X		X
HIV RNA			X		X
SOC Only					
Study Visit	X		X		X
Referral to standard prevention options	X		X		X
Rapid (blood-based) HIV test	X		X		X
Suspected seroconversion³					

¹Late visits for routine assessments will not be considered Protocol Violations, allowing flexibility during the COVID-19 pandemic

²This assessment will be done on all intervention participants at baseline

³See Figure 2

⁴Week 48 visits may occur between 40 and 56 weeks after Baseline

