-Hair sample (if CAB-LA received in last 120 days)			X		X	X		X						
-Stored plasma (from 2 cc sample above)		X	X	X	X	X	X	X						
Safety Labs														
-Pregnancy testing ¹	X	X	X	X	X	X	X	X	X	X	X	X	X	X
-ALT Monitoring ^{4, 5}	X		X*		X			X*			X*			X*
Adverse Event Monitoring	X	X	X	X	X	X	X	X	X	X	X	X	X	X
GBV Screening	X				X			X			X			X
Survey and IDI														
-Participant CAB-LA Survey and IDI ²	X				X			X						
-Provider and Clinic Staff DCP-LA Survey and IDI	X				X			X						
Costing³	X	X				X								
For participants who stop CAB LA before end of extension study														
-For 48 weeks from last injection: Recommend oral PrEP (TDF/3TC) to cover tail														
-Switch back to Q12 week visits - HIV RNA and pregnancy testing Q12 weeks														

¹For women who become pregnant, repeat pregnancy tests are not needed. Women who become pregnant during the study will be followed to delivery for assessment of mother and infant status

²Participant survey/IDI will be conducted at start of CAB-LA and Weeks 24 and 48 from time of CAB-LA start or discontinuation.

³Costing will occur between weeks 24-48.

⁴ALT Monitoring will occur at baseline, Week 24 for all participants. *Per provider discretion, ALT monitoring will occur at Weeks 8, 48, 72 and 96.

⁵Bilirubin and additional labs indicated will be tested in the case of ALT increase.

⁶HIV RNA will be drawn at CAB-LA reinduction, as described in Table 6.

⁷ Week 48 visits may occur between 40 and 56 weeks after Baseline; Week 96 visits may occur between 88 and 104 weeks after Baseline; only participants on CAB-LA at the Week 48 visit may take CAB-LA between weeks 48 and 96.

E. Extension Consent Process

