Less than or equal to 8-weeks	Administer 600-mg (3-mL) gluteal intramuscular injection of CAB-LA as soon as possible, then continue to follow the every 8-weeks injection dosing schedule.
Greater than 8-weeks	Restart with 600-mg (3-mL) gluteal intramuscular injection of CAB-LA, followed by a second 600-mg (3-mL) initiation injection 4-weeks later. Then continue to follow the every 8-weeks injection dosing schedule thereafter.

If third or subsequent injection is missed and time since prior injection is:	
Less than or equal to 12 weeks	Administer 600-mg (3-mL) intramuscular injection of CAB-LA as soon as possible, then continue with the every 8-weeks injection dosing schedule.
Greater than 12-weeks	Restart with 600-mg (3-mL) gluteal intramuscular injection of CAB-LA, followed by the second 600-mg (3-mL) initiation injection dose 4-weeks later. Then continue with the every 8-weeks injection dosing schedule thereafter.

4. Contraindications. CAB-LA is contraindicated in individuals:

- a. With unknown or positive HIV-1 status
- b. With previous hypersensitivity reaction to cabotegravir
- c. Receiving the following co-administered drugs for which significant decreases in cabotegravir plasma concentrations may occur due to uridine diphosphate glucuronosyltransferase:
 - i. Anticonvulsants: Carbamazepine, oxcarbazepine, phenobarbital, phenytoin
 - ii. Antimycobacterials: Rifampin, rifapentine

5. Drug Interactions

- i. **Use of Other Antiretroviral Drugs after Discontinuation of CAB-LA.** Residual concentrations of cabotegravir may remain in the systemic circulation of individuals for prolonged periods (up to 12 months or longer). These residual concentrations are not expected to affect the exposures of antiretroviral drugs that are initiated after discontinuation of CAB-LA
- ii. **Potential for Other Drugs to Affect CAB-LA.** Cabotegravir is primarily metabolized by UGT1A1 with some contribution from UGT1A9. Drugs that are strong inducers of UGT1A1 or 1A9 are expected to decrease cabotegravir plasma concentrations; therefore, coadministration of CAB-LA with these drugs is contraindicated
- iii. **Established and Other Potentially Significant Drug Interactions.** Information regarding potential drug interactions with cabotegravir is provided in **Table 8** below.

Table 8. Drug Interactions with CAB-LA

Concomitant Drug Class: Drug Name	Effect on Concentration	Clinical Comment

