- v. It is recommended that participants of child bearing potential taking CAB LA should use an effective contraceptive method during the study, through any additional extension phase and for 52 weeks after the last injection if transitioning off CAB-LA, to avoid pregnancy. Participants that are currently on a contraceptive method at CAB-LA start will be informed of the risks and benefits of CAB-LA during pregnancy, if they chose to stop using contraceptives. Participants not on a contraceptive method when starting CAB-LA will be informed about the risks and benefits to CAB-LA during pregnancy if they become pregnant. CAB-LA will not be given to women who are pregnant at time of initial injection; women who become pregnant after starting CAB-LA will be allowed to remain on CAB-LA during pregnancy, as deemed appropriate by their provider, and will be re-consented for additional follow-up of pregnancy and infant outcomes.
- vi. It is not known if cabotegravir is present in human breast milk, affects human milk production, or has effects on the breastfed infant. Participants who are currently breastfeeding will be informed of the risks and benefits in the consenting process, and unknown effects on infants of exposure to CAB-LA through breastmilk.
- vii. No dosage adjustment of CAB-LA is necessary for participants with mild (creatinine clearance 60 to <90 mL/min) or moderate renal impairment (creatinine clearance 30 to <60 mL/min). In participants with severe renal impairment (creatinine clearance 15 to <30 mL/min) or end-stage renal disease (creatinine clearance<15 mL/min), increased monitoring for adverse effects will be provided
- viii. No dosage adjustment of CAB-LA is necessary for participants with mild or moderate hepatic impairment

b. **Overdosage.** There is no known specific treatment for overdose with CAB-LA. If overdose occurs, the participant will be treated appropriately, and further CAB-LA continuation determined by the Investigator.

c. **Storage and Handling.**

- i. CAB-LA will be stored at 2°C to 30°C (36°F to 86°F) in the original carton until ready to use. Exposure up to 30°C is permitted, but freezing is not. CAB-LA cannot be mixed with any other product or diluent.
- ii. If the pack has been stored in the refrigerator, the vial will be brought to room temperature prior to administration (not to exceed 30°C [86°F]).

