- iii. Once the suspension has been drawn into the syringe, the injection will be administered as soon as possible, but may remain in the syringe for up to 2 hours. The filled syringes will not be placed in the refrigerator. If the medicine remains in the syringe for more than 2 hours, the filled syringe and needle will be discarded

d. **Possible Side effects:**

- i. Allergic reactions:
 - generally ill feeling
 - blisters
 - tiredness
 - muscle or joint aches
 - trouble breathing
 - fever
 - blisters or sores in the mouth
 - redness or swelling of eyes
 - swelling of the mouth, face lips or tongues
- ii. Liver problems
- iii. Depression or Mood Changes
- iv. Most Common Side Effects:
 - Pain, tenderness, hardened mass or lump, swelling, bruising, redness, itching, warmth, loss of sensation at the injection site, abscess, and discoloration
 - stomach pain
 - vomiting
 - diarrhea
 - muscle pain
 - headache
 - rash
 - fever
 - loss of appetite
 - tiredness
 - drowsiness
 - sleep problems
 - back pain
 - nausea
 - upper respiratory infection

G. Toxicity Management.

CAB-LA was very well tolerated in the registration studies. For this extension, SAEs will be captured in the intervention arm and Grade 3 and 4 AEs, and non-serious ADRs leading to withdrawal will be captured for participants on CAB-LA. Grade 3 and 4 AEs will be graded and recorded using the NIAID Adverse Event Grading of Severity scale (<https://rsc.niaid.nih.gov/clinical-research-sites/daids-adverse-event-grading-tables>). Clinical Adverse Events not identified elsewhere are described in **Table 10**. The Clinical Management Team (CMT) will be notified of SAEs as soon as possible and will be reported per regulatory guidelines as stated in **Table 9** below.

Table 9. Reporting Guidelines

Institution	Contact information	Type of Event	Reporting Timeframe	Reporting Method
UCSF IRB	UCSF Committee for Human Research [name] [contact]	SAEs/ Grade 3 or higher AEs that change the study risks or benefits, OR necessitates modification to the IRB-approved consent document(s), and/or the IRB-approved application/protocol	Within 10-working days of awareness	Via online reporting system

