All rash and suspected hypersensitivity events should be assessed with special attention to systemic symptoms, laboratory abnormalities, or mucosal involvement. Close clinical follow-up, including follow-up of laboratory abnormalities, and appropriate medical intervention, including referral to dermatologist as appropriate, should be instituted for these events. The prolonged release characteristics of CAB LA should be taken into consideration when these products are discontinued.

Participants should be instructed to contact the Investigator as soon as possible if they develop a rash or allergic symptoms on study.

Suicidal Ideation

There have been reports of depression and suicidal ideation and behaviours (particularly in patients with a pre-existing history of depression or psychiatric illness) in some people living with HIV being treated with integrase inhibitors. Depression has also been reported in individuals receiving cabotegravir for PrEP.

[figure not shown]
Participants should be monitored appropriately for any unusual changes in behaviour, before and during the course of the study. Participants with depressive symptoms or suicidal ideation and behaviours on CAB-LA should be promptly evaluated. It is recommended that the investigator consider mental health consultation or referral for participants who experience signs of suicidal ideation or behaviour.

Confirmation of suspected HIV infection

In cases of suspected HIV-infection, clinic staff are trained and use a seroconversion SOP for reference to proceed as depicted in Figure 2. For all cases, the clinical management team is

[figure not shown]
notified immediately, as simultaneous confirmatory testing, additional sample collection (including stored samples for further HIV testing and PK), counseling, and linkage to ART care are initiated.

Figure 2. HIV Seroconversion Algorithm and Sample Collection

For persons receiving CAB-LA, the following approach will be used for guidance on testing and administration of CAB-LA injections (Figure 3).

Figure 3. Algorithm for participants receiving CAB-LA Injections

H. Analyses

This section provides an overview of the stastical considerations.

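### After a participant stops CAB-LA, new non-serious Grade 3-4 adverse events have no explicit scheduled recording, although the drug tail is acknowledged to last a year or more

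*Protocol*

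**What the plan says.** All references are to Appendix 18 of the protocol unless stated.

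- **Capture rule (G, Toxicity Management).** SAEs are captured in the intervention arm. For lesser events the population narrows: "Grade 3 and 4 AEs, and non-serious ADRs leading to withdrawal will be captured for participants on CAB-LA".
- **Schedule for users (D, Table 6).** Adverse Event Monitoring is marked at every column from baseline to Week 96.
- **Schedule for stoppers (D).** "Participants that stop CAB-LA prior to the end of the extension time period will continue to be followed in the study", though not actively beyond 96 weeks, and a person "can return to an alternate DCP intervention if they decide to stop CAB-LA". The Table 6 lines for stoppers recommend oral PrEP for 48 weeks from the last injection and then say: "Switch back to Q12 week visits - HIV RNA and pregnancy testing Q12 weeks". Tables 5 and 5a, whose 12-weekly visits are for persons not receiving CAB-LA, have no adverse-event row.
- **No general fallback (main protocol, Section 10.2).** The study does not set out to collect all adverse events.
- **Recognition of exposure after stopping.** Section F says residual cabotegravir may remain for up to 12 months or longer. It also recommends contraception "for 52 weeks after the last injection if transitioning off CAB-LA". Section G adds, under Hypersensitivity: "The prolonged release characteristics of CAB LA should be taken into consideration when these products are discontinued".
- **Reason for recording.** The closing paragraph on human participants says Grade 3 and 4 events are recorded because CAB-LA was not yet approved in Uganda or Kenya. It names no population, visit or time window.

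**The concern.** The appendix acts on tail exposure for HIV testing, pregnancy and contraception, but not explicitly for adverse events. A person who stops, including one stopped for toxicity, still carries drug while attending study visits. If the capture rule and the stopper lines are followed as written, a new Grade 3 event at that time need not be asked about, graded or recorded. By the appendix's own grading table (Table 10), a clinical Grade 3 event means inability to carry out usual activities.

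The drug was unlicensed locally, and Section A says the extension to 96 weeks is meant to examine longer-term safety. Events not asked about at the visit cannot be reliably rebuilt by analysts afterwards. Because the wording is open, sites could also differ: some might carry on the Table 6 adverse-event row after stopping and others not.

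**Working it through.** The plan states no figure on this point, so the check sets the texts side by side and then counts visits.

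**1. Who is "on CAB-LA"?** The introduction writes "participants who are currently on CAB-LA may continue through the extension", and the Table 6 notes use the phrase for people on the drug at the Week 48 visit. Table 9 in Section G uses a different phrase, participants administered CAB-LA, for liver events, pregnancies and Significant Safety Issues. That contrast favours the current-user reading of the capture rule but does not prove it.

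**2. Is any adverse-event check scheduled after stopping?**

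- Table 6 marks adverse-event monitoring at 14 visits (baseline and Weeks 4, 8, 16, 24, 32, 40, 48, 56, 64, 72, 80, 88, 96) and injections at 13 (all but Week 96). The one extra check falls 96 − 88 = 8 weeks after the last scheduled injection, so it closes a dosing interval and does not cover the tail.
- The Table 6 lines for stoppers name three items (oral PrEP, HIV RNA, pregnancy testing); none is an adverse-event item.
- Tables 5 and 5a have no adverse-event row.

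**3. What is still covered after stopping?** SAEs in the whole intervention arm, which should include much clinical Grade 4, since Table 10 defines that grade as potentially life-threatening; known Grade 3+ liver events and Significant Safety Issues in anyone administered CAB-LA; pregnancy complications; and follow-up of toxicities already found. What remains is new, non-serious events, mainly clinical Grade 3.

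**4. How many tail visits are at stake per stopper?** Let w be the week of the last injection and E the end of participation, and assume CAB-LA starts at extension Week 0. Anchored on the last injection, with a 48-week tail:

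visits = floor((min(E, w + 48) − w) / 12)

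For example, E = 48 and w = 16 gives floor(32 / 12) = 2. The anchor is not stated, so two alternatives are shown for E = 48: 12-weekly visits counted from the next due injection, and the fixed Table 5 calendar (Weeks 12, 24, 36, 48).

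| Last injection, week | 0 | 4 | 8 | 16 | 24 | 32 | 40 |
|---|---|---|---|---|---|---|---|
| From last injection | 4 | 3 | 3 | 2 | 2 | 1 | 0 |
| From next due injection | 3 | 3 | 2 | 2 | 1 | 0 | 0 |
| Table 5 calendar | 4 | 4 | 4 | 3 | 2 | 2 | 1 |

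For instance, a last injection at Week 0 with the next due at Week 4 gives visits at Weeks 16, 28 and 40, so 3.

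For E = 96, which is conditional and needs re-consent, anchoring on the last injection gives 4 for w up to 48, then 3 at Week 56, 2 at Weeks 64 and 72, 1 at Week 80 and 0 at Week 88. Replacing 48 by 52 weeks in the formula leaves all these last-injection counts unchanged.

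The range is therefore roughly 0 to 4 visits. The number of stoppers and the event rate are not given; the 593 in Table 1 is only the cap on people eligible for CAB-LA.

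**The case against.** The strongest reply is that this is an ambiguity, not an exclusion. The uses of "on CAB-LA" that point to current users carry their own time qualifier, and the capture rule has none. Table 6 is headed for CAB-LA users, is indexed from the first injection and contains the stopper lines, so a site could carry its adverse-event row forward. The closing statement on recording Grade 3 and 4 events is not limited to current users. That much stands: the phrase is undefined. But nothing tells a site to continue the row, and the closing statement sets no visit or window.

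A reader might infer that nobody is in touch with stoppers about side effects. The documents do not support that:

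- Those who take the recommended oral PrEP have tolerance reviewed at least every 3 months (main protocol, Section 9.2.1.5).
- Section G asks for monitoring of unusual changes in behaviour during the study, and for participants to report rash or allergic symptoms.
- Section F provides close side-effect monitoring in pregnancy and breastfeeding, up to 8 weeks post-partum.
- Table 6, footnote 2, places surveys and interviews at Weeks 24 and 48 from start or discontinuation.
- Section 9.2.1.4 and Appendix Table 3 offer a clinician's telephone number and a 24-hour hotline.

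These contacts make it likelier that a serious problem surfaces, but none records and grades new Grade 3-4 events in stoppers generally.

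A reader might also infer that mandated regulatory reports would be missed. Table 9 does not clearly require individual reporting of non-serious Grade 3 events: its rows concern serious or unexpected events, harm, liver events, pregnancies, and events that change risk or consent.

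Finally, the information gained would be limited. Section H plans no adverse-event rate analysis, the section G rule does not extend Grade 3-4 capture to controls, and stoppers are advised to take oral PrEP, which confounds attribution. This lowers the priority but does not remove the case for recording.

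**Conclusion.** The point holds in a narrow form. New non-serious Grade 3-4 events, mainly clinical Grade 3, first arising after CAB-LA is stopped have no explicit scheduled adverse-event recording, at a time when the appendix itself recognises residual drug. This rests on reading "on CAB-LA" as current users, which is the most natural reading but not a stated definition, and on sites following the stopper lines as written.

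The size is about 0 to 4 visits per stopper without a named adverse-event check, for an unknown number of stoppers and an unknown event rate. The loss is to the safety record. The primary covered-time endpoint is unaffected. It would be wrong to conclude that safety follow-up ends on stopping. This is a cheap improvement of low-to-moderate priority; confidence is medium.

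**What to change.** Make two edits to Appendix 18:

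1. In Section G, define the population for Grade 3-4 capture as participants who have received CAB-LA, from first injection until 48 weeks after the last injection or end of study participation, whichever is first. The 48 weeks match the tail period in Table 6. Fifty-two weeks would also be acceptable, though that figure appears in the appendix only as contraception advice.
2. In the stopper lines of Table 6, add the existing adverse-event form to the 12-weekly visits.

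It would help to state that tail time after study end is not observed. Separate on-injection and tail listings are optional.

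The cost is a few minutes per visit and some extra adverse-event reports, with no new visit, test or analysis. Laboratory-only events would still be missed, because no ALT is scheduled for stoppers. Tail time after study end would stay unobserved, and attribution would remain confounded by oral PrEP. If capture through the tail was already intended, the edits simply make that plain to sites.
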